Continuous Glucose Monitoring with a Low Carbohydrate Diet to Reduce Weight in Patients with Pre-Diabetes

NCT: NCT03695913

Date of Last IRB Approval: March 21, 2019

Project Title: Continuous Glucose Monitoring with a Low Carbohydrate Diet to Reduce Weight in Patients with Pre-Diabetes

Protocol Number: HUM00145667

March 21, 2019

List of Personnel:

Name	Title	Dept.	Role	
[name]	[name]	Principal Investigator	
[name]	Assistant [name]	Informatics/eHealth	
[name]	[name]	CGM/Diabetes Expert	
[name]	Research Manager	Family Medicine	Administrative	
[name]	Clinical Researcher	Family Medicine	Informatics Design/Communication	
[name]	Assistant [name]/Mixed Methods	Qualitative interviewer and coder	
[name]	Assistant [name]	Health Economist	
[name]	[name] Expert	
[name]	[name]	Statistician	
[name]	Research Coordinator	Family Medicine	Research Coordinator/Medical Assistant/CGM Expert	
[name]	Resident	Family Medicine	Research Staff	
[name]	Resident	Family Medicine	Research Staff	
[name]	Research Coordinator	Family Medicine	Research Staff	
[name]	Registered Dietician	Family Medicine	Registered Dietician	
[name]	Research Coordinator	Family Medicine	Research Staff	
[name]	Medical School Student	Family Medicine	Research Staff	

Abstract

Background

Type 2 Diabetes is preventable yet few people diagnosed with pre-diabetes attend diabetes prevention programs. New strategies are needed to support people with pre-diabetes who are working to reduce their risk of converting from pre-diabetes to type 2 diabetes. Lower cost continuous glucose monitoring (CGM) technology may facilitate supervised and clinic-based approach to diabetes prevention.

Objective

The objective of this single arm pilot and feasibility study is to show that CGM feedback combined with a low carbohydrate diet can reduce the percentage of time CGM readings are above the normal range in patients with pre-diabetes.

Methods

We will recruit 10-15 adult pre-diabetic patients from the Michigan Medicine, Family Medicine clinic at the Livonia Health Center. Participants will be identified by chart review and invited to participate by letter and screened for eligibility by phone call. Eligible participants will attend a baseline visit and 2 follow up visits at the clinic. They will wear two CGM sensors for a total of 20 days of glucose monitoring and they will receive instruction in low carbohydrate eating. Primary outcome will be participant satisfaction with secondary outcomes including feasibility, weight change, % of time glucose above 140, side effects of low carbohydrate eating and qualitative participant experience.

Impact/Implications

Through this study we will demonstrate the feasibility using CGM with a low carbohydrate diet to reduce weight and risk of developing diabetes in patients with pre-diabetes.

1.0 Significance

Type 2 Diabetes is a preventable disease, but incidents of diabetes continue to increase worldwide. New strategies are needed to support people with pre-diabetes who are working to reduce their risk of converting from pre-diabetes to type 2 diabetes. Individualized treatment that incorporates feedback to the patient about their glycemic response to dietary choices may prove to be effective in helping patients change their diets. Newer low cost and user friendly continuous glucose monitoring (CGM) technology, costing approximately \$25.00 for 10 days of continuous monitoring with real time feedback may facilitate diet and exercise behavior change. This approach which is initiated during a one-on-one clinical encounter rather than in a stand-alone behavioral group class incorporates close clinical but remote monitoring and lower carbohydrate strategies. Results from this study will provide pilot and feasibility data to support a large grant application to NIH.

Specific Aim #1: Determine if CGM feedback combined with a low carbohydrate diet can reduce the percentage of time CGM readings are above the normal range in patients with pre-diabetes.

Specific Aim #2: Test the feasibility and acceptability of having patient with pre-diabetes wear CGM sensors and record diet, exercise and side effects on a low carbohydrate diet.

Specific Aim #3: To determine if cravings and hunger correlate with glucose below the normal range as detected by CGM in patients with pre-diabetes.

2.0 Originality

The diabetes prevention program incorporates a traditional high-carbohydrate low-fat diet. Our previous pilot work has demonstrated that a lower carbohydrate diet plan can improve weight loss in patients with pre- diabetes. However, as with all behavior modification programs, adherence is a problem. By incorporating CGM feedback and monitoring into the lower carbohydrate program, patients will have the support they need to effectively change their behavior. While it is difficult to do the intensive training and support for dietary change in the context of a physician visit, the remote monitoring using CGM makes it more feasible to use an efficient team- based approach to individualized behavior change counseling in a clinical context.

Previous Work: [name] was the Principle Investigator on the VA's National Diabetes Prevention Program Clinical Demonstration Project and she has published 10 peer reviewed original research papers related to diabetes prevention in the last 24 months. In addition, our low carbohydrate diabetes prevention research team recently completed a pilot and feasibility study of a low carbohydrate diabetes prevention intervention in which we enrolled 22 patients and which resulted in a mean weight loss of 9.4 pounds (SD 10.7), mean reduction in A1C: 1 (SD .2). Qualitative results support feasibility and acceptability of low carbohydrate diet for diabetes prevention

3.0 Methods

3.1 Study Design: Single arm pilot and feasibility study.

Outcomes;

Primary: Participant Satisfaction	Items on f/u survey and qualitative interview			
Secondary:				
Feasibility	Successful recruitment, Successful sensor wears time			
	20/22 days, Data retrieved from sensor successfully			
Weight Change	Weight at final visit – weight at 2 nd visit			
Knowledge of Low Carbohydrate Eating	Low Carb Knowledge Scale – final - baseline			
Cravings and Hunger	Ratings on food logs			
Intention to continue Low Carbohydrate eating	final survey question			
Side effects of CGM wear, Low Carbohydrate eating	Side effect log			
Utility of CGM feedback for changing diet	Qualitative Interview			

3.2 Study Population and Recruitment:

As identified though MiChart and Data Direct searches, 10-15 adult Michigan Medicine patients who qualify based on inclusion and exclusion criteria will be contacted via US Mail regarding their participation in our study. This letter will explain the study and its requirements and will be accompanied by an opt-out postcard that can be returned if the patient no longer wishes to be contacted. Those who do not return the postcard will be contacted via telephone with further information about the study. Recruiting will also be accomplished through a posting on the UM Health Research website as well as printed materials such as fliers and brochures. Interested and eligible participants will be scheduled to attend a one-on-one in-person baseline visit with the study coordinator at Livonia Health Center.

3.3 Inclusion/Exclusion Criteria:

- 21+ years of age
- A1C 5.7 to 6.4
- No Diabetes medication including Metformin
- BMI >30
- Must speak, read, and write in English
- Must have a phone
- Must have a computer
- Interested in changing diet to improve health
- No current pregnancy
- No previous Bariatric surgery
- Must not classify as either Vegan or Vegetarian
- Must be a patient at the Livonia Health Center

3.4 Informed Consent: At the baseline assessment the Research Coordinator will thoroughly review the Informed Consent document with the participant. If valid informed consent is freely given the baseline data collection will begin.

3.5 Phase One, In-Person Appointment:

- Obtain a valid informed consent
- Baseline measurements including weight, height, and blood pressure

- Power point presentation outlining the study and the participant's role in Phase One.
- Teaching on continuous glucose monitor and how it will be used to monitor their blood glucose reactions to the food that they consume.
- Application of an Abbott Libre Pro sensor (no real time feedback) to the backside of the participant's nondominant arm.
- The participant will be asked to:
 - o leave the sensor in place for a period of 11 days
 - o complete a food log during that time, documenting what they consume
 - o Rate their postprandial hunger and fatigue 2 hours after eating
- Participants will be given a wrapped copy of the book, "Always Hungry" by [name] and asked not to open the book until after they receive their health check phone call on Day 5.
- Participants will then be given the Study Coordinators contact information
- Appointments for the second and third meeting will be made.

3.6 Health Check Phone Call: Approximately 5 days after each new sensor is p

- A member of the study team will call the participant to ensure that the participant is experiencing no ill effects from wearing the sensor.
- The study team member will also answer any questions that the participant may have regarding the sensor or the study in general.
- The study team member will then ask the participant to open their copy of the book, "Always Hungry" by David Ludwig and encourage the participant to read chapters 1-5.

3.7 Phase Two, Intervention Appointment: Approximately 11 days after their first appointment:

- Participants will return to the Livonia Health Center for a second one-on-one meeting.
- Weight, and blood pressure will be repeated.
- Participants will then take a brief survey.
- The Abbott Libre Pro sensor will be removed.
- Data captured by the sensor will be uploaded and printed for the participant.
- All uploaded data will be reviewed with the participant and compared to their completed food Log.
- Participants will be shown a Power Point presentation that discusses their role in Phase Two.
- Abbott Libre **personal** sensor (with meter for real time feedback) will be applied to the back of the participants non-dominate arm.
- Participants will be taught about carbohydrates and the benefits of eating a low carbohydrate diet.
- Participants will be given a new food log and asked to:
 - o document the food that they consume
 - o rate their postprandial hunger and fatigue two hours after eating
 - o document their blood sugar before and two hours after eating
- Participants will be given multiple resources to assist them in determining how many carbohydrates are in the foods they consume.
- Participants will be given the book entitled, "The Calorie King, Calories, Fat, and Carbohydrates," which lists the calorie, fat, and carbohydrate content of various foods.
- Possible side effects of low carbohydrate diet will be discussed with the participant and information on how to mitigate the effects of the diet will also be provided.

- Patients will be instructed to fill out a side effect log as well as their diet log during this phase.
- Participants will complete an information sheet, voluntarily suppling their address as well as any information about food allergies they may have.
- Participants will choose two recipes from a group of five options that they would like to make for themselves and/or their immediate family.
- **3.8 Grocery Delivery:** Approximately two days following the participants second visit all of the ingredients for one of their chosen recipes will be delivered to the address provided. All of the ingredients for the second recipe that the participant has chosen will be delivered approximately five days later.
- **3.9 Follow-Up Visit:** Approximately 11 days after the intervention visit:
 - Participants will have the second sensor removed.
 - Data obtained by the sensor will be uploaded and printed out for their review.
 - Participant's data will be compared to their completed food log.
 - Participants will also be provided with a letter to take to their Primary Care Physician (PCP) explaining the study and asking for a prescription for an Abbott Libre personal sensor so that the participant may continue tracking their blood glucose levels following the study.
 - Participants will take the "Completion Survey"
 - Participants will receive either a check or a voucher for \$25.00 for completing the survey and all three of their in-person appointments.
 - Participant wishes to continue wearing a CGM and has found that it has been an effective way to assist them
 in consuming a low carbohydrate diet, they will be given a letter addressed to their Primary Care Physician
 asking for a prescription to continue using the Abbott Libre personal CGM sensors and reader.
- **3.10 Semi-structured qualitative interview:** After the participant has completed all three visits with the Research Coordinator and have worn both CGM sensors, they will receive a telephone call from the studies mixed methods interviewer who will conduct a semi-structured qualitative interview. Each participant will be asked a series of questions concentrating on their satisfaction with the CGM sensors and devices, how their diet has been effected by wearing the CGM sensors, and how they feel about having been diagnosed with pre-diabetes.
- **3.11 6-month Follow-up Telephone Interview:** A member of the research team will call each participant six months after they have completed all three appointments to conduct a second semi-structured qualitative interview. Each participant will be asked a series of questions designed to ascertain whether or not the study has had continued impact on their diet and ability to prevent the transition to Type 2 Diabetes. The participant will be asked questions like whether or not they have continued their effort to avoid carbohydrates and whether or not they have worked with their Primary Care Physician to obtain their own personal continuous glucose monitor.

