3.5.2 Baseline Survey

- Participants will be asked to complete a brief, survey of approximately 45 questions over a period of approximately 15 minutes.
- Survey will contain questions relating to: diabetes and diet experiences, hunger and cravings, post-prandial fatigue, carbohydrate knowledge, current attitudes about health, and numeracy.

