3.5.7 Phase One Food Log

- Participants will be asked to complete a daily food log
- Log asks participants to write down the food that they eat and what time they are it.
- Participants are asked to record their food intake in general terms rather than breaking it down
 in to chloric content, Protein content, or carbohydrate content
- Approximately 2 hours after eating participants will also document their level of hunger and post-prandial fatigue

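### The outcomes table takes cravings from the food logs, but neither log procedure asks participants to rate cravings, leaving half of Aim 3 without meal-level data

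*Protocol*

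**What the plan says.** Specific Aim 3 (protocol, 1.0 Significance) reads: "To determine if cravings and hunger correlate with glucose below the normal range as detected by CGM in patients with pre-diabetes". It names no instrument. The outcomes table in section 3.1 does: the source for the secondary outcome of cravings and hunger is "Ratings on food logs".

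There are two logs, one per sensor period, and each is described in a summary and in a detailed procedure.

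- Phase One, summary (3.5): "Rate their postprandial hunger and fatigue 2 hours after eating".
- Phase One, detail (3.5.7): "Approximately 2 hours after eating participants will also document their level of hunger and post-prandial fatigue". The log also has participants "write down the food that they eat and what time they are it".
- Phase Two, summary (3.7): "rate their postprandial hunger and fatigue two hours after eating", together with blood sugar before and two hours after eating.
- Phase Two, detail (3.7.6): the same two ratings, plus glucose on waking, at bedtime, before each meal or snack and two hours later.

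Cravings are otherwise named as collected only in the baseline survey (3.5.2), whose topics include "hunger and cravings, post-prandial fatigue, carbohydrate knowledge, current attitudes about health, and numeracy". At the second visit, "Participants will then take a brief survey", and there is a final survey at the third visit (3.9). The contents of these two surveys are not listed.

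**The concern.** The protocol names an outcome and its source, but the procedures for that source do not ask for half of the outcome. Loose wording is an unlikely explanation, because the baseline survey topics treat cravings, hunger and fatigue as distinct. As described, the logs collect a rating that is not a listed outcome (fatigue) and are not said to collect one that is (cravings).

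What is at stake is whether Aim 3 can be answered for cravings at the level where the question makes sense. Low glucose on CGM is a momentary event, so the natural analysis sets a rating taken at a known time against the sensor reading around that time. A survey score cannot be placed that way. This is a matter of data collection, so a later analysis plan cannot repair it.

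There is a smaller, related issue in Phase Two. Section 3.7.6 has participants log glucose at the same moment as they rate hunger and does not say which comes first, and the reader shows them the value (3.7.7). Seeing the number first could colour the rating that Aim 3 then correlates with it.

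**Working it through.** The main check is a comparison of text; the protocol gives no figure of its own to reproduce.

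**Rated items in each log description**

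| Description | Hunger | Fatigue | Cravings |
|---|---|---|---|
| Phase One summary (3.5) | yes | yes | no |
| Phase One detail (3.5.7) | yes | yes | no |
| Phase Two summary (3.7) | yes | yes | no |
| Phase Two detail (3.7.6) | yes | yes | no |

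Hunger is requested in 4 of 4 descriptions, so for 2 of 2 logs. Cravings are requested in 0 of 4, so for 0 of 2 logs. The outcomes table says the logs supply both.

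**Other possible sources.** The baseline survey covers cravings but is given once, at the first appointment. The side effect log (3.7.8) does not mention cravings. The contents of the visit-2 and final surveys are unstated, and the outcomes table does not name any survey as the source.

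**What the logs allow as described.** Eating time is recorded and the hunger rating follows about two hours later, so its approximate time is known. The logs are also compared with the sensor reports (3.7 and 3.9). Hunger can therefore be set against CGM glucose meal by meal; cravings cannot.

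**How much the fallback could show.** Suppose cravings came only from a survey, with one craving score and one low-glucose summary per participant. The planned size is 10 to 15 (3.2). The protocol does not propose this analysis; it is shown only to size what would be left. It assumes an ordinary Pearson correlation and complete data.

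Smallest |r| significant at two-sided 5%: r = t / √(n − 2 + t²).
- n = 10, 8 df, t = 2.306: 2.306 / √(8 + 5.318) = 0.632
- n = 15, 13 df, t = 2.160: 2.160 / √(13 + 4.666) = 0.514

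True r needed for 80% power, by the Fisher z approximation: r = tanh[(1.960 + 0.842) / √(n − 3)].
- n = 10: tanh(2.802 / √7) = tanh(1.059) = 0.785
- n = 15: tanh(2.802 / √12) = tanh(0.809) = 0.669

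Only a strong association would be detectable.

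**The case against.** The best counter-argument is that this is an omission rather than a contradiction. The outcomes table states positively that cravings are rated on the logs, and the procedures never say that hunger and fatigue are the only ratings. The summaries also leave things out elsewhere: the waking and bedtime glucose readings in 3.7.6 are absent from summary 3.7. A missing bullet is therefore imperfect evidence of a missing item on the form, and the form is not reproduced in the protocol. This stands as a limit: what is shown is that no craving rating is described, not that none exists. It does not remove the problem, because the detailed procedures are what staff would work from, and they omit the item as consistently as the summaries do.

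The harm is also narrow: half of one secondary outcome in a small single-arm pilot whose primary outcome is satisfaction. That is true, and the hunger half of Aim 3 is intact. But Aim 3 is one of only three aims, and ratings not taken at the time cannot reliably be recovered.

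The correlation figures do not measure the inconsistency itself and would apply to any correlation of this size. That is fair; the conclusion does not depend on them.

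The order of scanning and rating is a side issue. Phase One gives no real-time feedback, so its hunger ratings are unaffected. No size can be put on any bias in Phase Two.

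**Conclusion.** The concern holds. The outcomes table says that both food logs yield craving ratings, whereas the procedures ask for hunger on 2 of 2 logs and cravings on 0 of 2. As written, the craving half of Aim 3 has no described meal-level measurement. Any participant-level substitute from survey data would rest on 10 to 15 points and could detect only a true correlation of about 0.79 (n = 10) or 0.67 (n = 15) with 80% power.

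The conclusion rests on the procedures being the basis for the log forms, which are not shown. If the forms already include cravings, the defect is one of text alone. It should be fixed before logs go to participants. The scan-order point is minor, and no size is claimed for it.

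**What to change.** First check the log forms. If they already carry a craving item, add it to 3.5, 3.5.7, 3.7 and 3.7.6; this costs a text edit only.

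If they do not, choose one of two routes.

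1. **Add a craving rating beside hunger on both logs, and say so in those four sections.** No new device or visit is needed. Ratings per eating occasion rise from 2 to 3. Assuming 3 to 5 eating occasions a day (the protocol gives no figure), the extra entries are 3 × 11 = 33 to 5 × 11 = 55 per 11-day log, or 66 to 110 per participant over both logs. That burden bears on the acceptability tested in Aim 2 and should be weighed against it.
2. **Remove cravings from Aim 3 and from the outcomes table.** This adds no burden but gives up that half of the aim.

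Renaming the source in the table as the surveys would also restore consistency, but the survey contents would then have to be stated, and the analysis would be the weak participant-level one above.

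Separately, one sentence in 3.7.6 could ask participants to write the two-hour rating before scanning. It costs almost nothing and reduces expectation bias, but does not remove it, since participants will have seen earlier readings.

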3.5.4 Abbott Freestyle Libré Pro and Sensor

- Participant will wear an Abbott Libre Pro sensor on their arm for a total for 11 days
- The first day the sensor will be adjusting to the participants' unique physiology so that the most accurate blood glucose levels and estimated A1c will be reported.
- The participant will receive no real time feedback.

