3.6 Health Check Phone Call

- On Day 6 of the participant wearing the first sensor as well as on day 6 of participant wearing the second sensor
- Participants will receive a phone call from the study team's mixed methods qualitative Interviewer at a time prearranged when making other appointments
- Participant will be asked a brief series of questions designed to ensure that the participant is experiencing no ill effects from wearing the CGM sensor on their arm
- Interviewer will also ask questions regarding the participant's food log to ensure their understanding as well as to remind them to be documenting honestly
- Participants will be asked to unwrap their copy of Always Hungry? And begin reading chapters 1-5.

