3.7.3 Sensor Scanning and Removal

- Using the Abbott Freestyle Libre Pro reader the study coordinator will scan the participants' sensor
- Sensor will then gently be removed from the participant's arm
- The area where the sensor was applied will be wiped down with an alcohol wipe to ensure that the area around the small puncture wound created by the microfilament remains free from any contaminants
- The Reader will be connected to the computer via USB and the sensor data will be uploaded by the Abbott Libre Pro software, Libre View.

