3.7.8 Side Effect Log

- Participants will be asked to document and side effects that they experience and when they occur on a side effect log.
- This log will be reviewed so that suggestions can be made about how they could further alter their diet to relieve these side effects.

3.7.9 The CalorieKing: Calorie, Fat, and Carbohydrate Counter (2017):

- All participants will receive a copy of the book, The CalorieKing: Calorie, Fat, and Carbohydrate Counter (2017).
- This book will assist the participants in deciding which foods to eat and which to avoid while eating in such a way as to reduce carbohydrate consumption.

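### The side effect log, the only source section 3.1 names for CGM side effects, is first issued at the Phase Two visit and so misses the first sensor wear, about 11 of 22 wear days

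*Protocol*

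**What the plan says.** The outcome table in section 3.1 lists "Side effects of CGM wear, Low Carbohydrate eating" as a secondary outcome, and the side effect log is the only entry beside it. Where several sources are intended, the table says so: the primary outcome, satisfaction, has both survey items and the qualitative interview.

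The log appears in two procedural places, and both belong to Phase Two. Section 3.7 states: "Patients will be instructed to fill out a side effect log as well as their diet log during this phase". Section 3.7.8 adds: "Participants will be asked to document and side effects that they experience and when they occur on a side effect log".

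The first sensor wear comes before this. Section 3.5.4 states: "Participant will wear an Abbott Libre Pro sensor on their arm for a total for 11 days". At the Phase Two visit that sensor is scanned and taken off (section 3.7.3: "Sensor will then gently be removed from the participant's arm"). The Phase One tasks in section 3.5, in both the summary and the detailed version, include a food log and ratings of hunger and fatigue, but no side effect log.

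The feasibility row of section 3.1 sets the total wear against which success is judged: "20/22 days, Data retrieved from sensor successfully".

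**The concern.** The outcome as worded covers side effects of wearing the sensor, and each participant wears two sensors. A form handed out when the first sensor comes off cannot prospectively record what happened under it. A report of CGM side effects drawn from the named source would describe the second wear only and could under-count.

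The omitted wear is also the more informative one for sensor effects. Low carbohydrate teaching begins at the Phase Two visit, so during the logged wear the sensor and the diet change run together, and a logged symptom may be hard to attribute to one or the other. The first wear is the only one before that teaching, although the diet book is opened after the health check call, so only the days before the call are free of all diet material.

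Specific Aim 2 concerns the feasibility and acceptability of CGM wear in this population, and section 1.0 says the results are to support a larger grant application. Tolerability of the sensor is therefore part of what the pilot should deliver.

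**Working it through.** **Inputs**
- First wear: 11 days (sections 3.5 and 3.5.4).
- Second wear: about 11 days, from the Phase Two visit to the follow-up visit (section 3.9).
- Total in the wear-time criterion: 22 days (section 3.1).
- Participants: 10 to 15 (Abstract and section 3.2).
- Health check call in Phase One: Day 5 in the summary of section 3.5, Day 6 in the detailed section 3.6.

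**The protocol's own figure.** 11 + 11 = 22 days, which reproduces the denominator in section 3.1.

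**Coverage by the named source**
- Wear days outside the log: 11 / 22 = 50%.
- Sensor wears outside the log: 1 of 2.
- On the Abstract's 20 days of monitoring, split evenly between sensors (an assumption): 10 / 20 = 50%.
- With 10 participants: 10 × 11 = 110 of 10 × 22 = 220 wear-days, and 10 of 20 wears.
- With 15 participants: 15 × 11 = 165 of 15 × 22 = 330 wear-days, and 15 of 30 wears.

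The last two lines are the same 50% expressed for the whole study; they are not further evidence.

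**Sensitivity: counting the Phase One call as a source.** Assume its answers fully cover every day up to the call.
- Call on Day 5: (5 + 11) / 22 = 16 / 22 = 72.7% covered; 6 days (27.3%) left.
- Call on Day 6: (6 + 11) / 22 = 17 / 22 = 77.3% covered; 5 days (22.7%) left.
- Over the study: from 5 × 10 = 50 to 6 × 15 = 90 participant-days left.

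**Diet half of the outcome.** Diet teaching starts at the visit at which the log is issued, so the timing of the log fits diet effects.

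**After the change.** A log issued at both visits covers 22 / 22 = 100% of wear days.

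**What cannot be computed.** The protocol gives no rate of sensor side effects. The number missed lies anywhere between none and all of those that occur in the first wear.

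**The case against.** The strongest reply is that the log was only ever a diet tool. In section 3.7 the instruction follows directly on the discussion of diet side effects. Section 3.7.8 gives its use: "This log will be reviewed so that suggestions can be made about how they could further alter their diet to relieve these side effects". The Abstract and Specific Aim 2 mention side effects of the diet only. On this reading the fault is an over-broad label in one table row, and a count of wear days does not measure it. This is a fair reading, but it does not remove the problem: section 3.1 would then be wrong as written, and the CGM half of the outcome would have no named source at all.

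The second reply is that sensor effects in the first wear are picked up elsewhere. The detailed section 3.6 provides a call with questions "designed to ensure that the participant is experiencing no ill effects from wearing the CGM sensor on their arm". The coordinator sees the site when the sensor is removed, there is a brief survey at the second visit, the later interview covers satisfaction with the sensors, and participants hold the coordinator's contact details. These contacts make it less likely that a troublesome effect goes unnoticed, and the days-left figures above give no credit for the removal visit. But section 3.1 names none of them for this outcome, the protocol does not describe any of them as recording side effects, and the content of the survey is not described.

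The third reply is that the stakes are small, and this stands. The study is a single-arm pilot, no visible test or decision rule uses this outcome, and each participant who completes Phase Two has one logged wear, with the sensor applied by the same technique.

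Nor can the point be left to an analysis plan: when a form is handed out is a study procedure, and analysis cannot recover data that were not collected.

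**Conclusion.** The concern holds. As written, the only source named for CGM side effects omits the first sensor wear: about 11 of 22 days (50%) and one of two sensors per participant. If the Phase One call were recorded and counted with full recall, 5 to 6 days (23 to 27%) would still be uncovered. An under-count is possible but not demonstrated.

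The consequence is limited to the CGM half of one secondary outcome in 10 to 15 people. The change is worth making because it affects which data are collected and costs very little.

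The conclusion takes section 3.1 at its word that the log serves CGM effects; if it does not, the fault is a missing source, not partial coverage. It also rests on the visible text: a part of the protocol between sections 4.0 and 6.1 was not available.

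**What to change.** Decide what the log is for, and bring section 3.1 into line with the Abstract, Specific Aim 2 and sections 3.5 to 3.7.

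- **If it serves both kinds of side effect:** issue the existing log at the first visit and collect it at the second. Record the answers to the health check calls, and name the call in section 3.1 as a second source. Report sensor and skin effects descriptively over both wears.
- **If it serves diet effects only:** say so in section 3.1, and name there a separate source for CGM effects that covers both wears.

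The first option costs 10 to 15 extra copies of an existing form, a few minutes of each participant's time, and a short amendment to sections 3.1, 3.5 and 3.6. Log coverage of wear days rises from about 50% to 100%.
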